2. INVESTIGATIONAL PRODUCT

2.1 ACTIVE INGREDIENT, PHARMACOLOGIC CLASS, STRUCTURE

The active ingredient in the drug product bermekimab is MABp1, a recombinant human IgG1 monoclonal antibody specific for human interleukin-1 α (IL-1 α). The entire bermekimab heavy and light chain sequences are identical to those found in naturally-occurring human IgG1 κ , with the light and heavy chain variable regions being identical to those originally expressed by a peripheral blood B lymphocyte that was obtained from a healthy individual.

Figure 1.0: Bermekimab Antibody

The bermekimab primary glycoform has a molecular weight of 148.1 kilodaltons. Like all IgG1 molecules, the heavy chains are joined at their hinge regions through two disulfide linkages, and each heavy chain is joined to one light chain through one disulfide linkage between their CH₁ and CL domains respectively.

The main isoform has a pI of about 9.2 and comprises about 70-80% of the total isoform population in all lots that have been manufactured to date, as determined by capillary isoelectric focusing. The heavy chain CH₂ domains are glycosylated primarily with the oligosaccharide structure shown in Figure 1.0, as determined by mass spectroscopy of the cleaved glycans. The glycosylated residue (Asn-302 as numbered from the N-terminus of bermekimab) has been determined by peptide mapping to be in the same highly conserved N-linked glycosylation site as found in endogenous IgG1 (Asn-297 according to the generic numbering system). Similarly, the primary glycan, commonly referred to as G0F, is the same as that found on about 22% of endogenous human IgG molecules²⁷.

The entire bermekimab heavy and light chain sequences are identical to those found in naturallyoccurring human IgG1 κ , with the light and heavy chain variable regions being identical to those originally expressed by a peripheral blood B lymphocyte that was obtained from a healthy individual.

Endogenous anti-IL-1 α antibody has been reported in 5% to 28% of healthy serum or plasma samples^{28,29}. It has been measured in cord blood, children and adults³⁰. The anti-IL-1 α antibodies measured in human plasma have been strictly of the IgG class, particularly IgG1, IgG2, and IgG4. Relatively equal distribution is seen in male and female plasma³¹. Binding affinities reported for endogenous anti-IL-1 α antibodies, ranging from 4 to 16 pM.

It is important to point out that affinity maturation had already taken place in the human host, and therefore no *in vitro* affinity maturation was required to increase the natural binding affinity of bermekimab. Also important is the fact that, unlike most other therapeutic IgG products, for which the Fc regions are derived from a rare human allele, XBiotech's product includes a heavy chain in which the constant (CH) region represents an allele found in approximately 70% of the human population. These two features should make for a drug product with reduced potential for immunogenicity.

2.2 DRUG PRODUCT (BERMEKIMAB 200 MG/ML) DESCRIPTION

XBiotech's dosage form is a sterile liquid formulation of 200 mg/mL bermekimab in a stabilizing isotonic subcutaneous formulation buffer at pH 6.2-6.5 containing non-active ingredients of low concentrations of sodium phosphate, citric acid and trehalose. The drug product is packaged in pre-filled syringes. Drug product in syringes is stored at 2-8°C and is recommended to be protected from light.

2.3 STORAGE

The recommended storage condition is at 2-8°C.

2.4 STABILITY

The drug product is formulated in a buffer in which most of the tonicity comes from trehalose rather than salt. Trehalose is an effective stabilizer against oxidation, aggregation, thermal, and mechanical stress. Citrate was selected as the buffering agent due to its antioxidant properties.

Extensive stability data indicates that the drug product is very stable, even under thermally and mechanically stressed conditions. Short excursions to room temperature have shown no negative effect on the product. However, the study treatment products are not to be frozen at any time. The 200 mg/ml drug product is labeled with a 12-month retest date. Every lot of 200mg/ml dosage form is also subjected to ongoing stability analysis per ICH guidelines.

2.5 DESIGNATED INDIVIDUAL FOR DRUG ADMINISTRATION

To ensure that no unintentional unblinding occurs during study drug administration, at lease one qualified individual will be designated at each study site to perform all preparation and injection of the investigational product. The designated injector(s) should have no other contact with the participant during the study, should not discuss the participant's treatment with the participant, participant's caregiver, or other site personnel at any time, and will not be permitted to review the participant's medical records, questionnaires, or the electronic CRF prior to each injection. The designated injector(s) should be documented in the source documents at each visit.

2.6 METHOD OF ADMINISTRATION

Following two initial 800 mg loading doses of either bermekimab or placebo, patients in all arms will receive 400 mg of either bermekimab or placebo via subcutaneous injection administered weekly. Each injection should be administered at least one inch from previous injection sites.

* At least 45 minutes prior to injection, remove the pre-filled syringe from

refrigeration

Lay the syringe on a flat surface and let it naturally warm to room temperature before injection. It may also be warmed by holding in hand. Do not heat the syringe.

Materials

Bermekimab pre-filled syringe for injection, warmed to room temperature* Sterile alcohol wipes Band-aids, along with 2x2 gauze bandages and paper tape Latex-free gloves

Injection Site

Abdomen, at least 2 inches away from the belly button

(Note: avoid areas where the skin is burned, scarred, hardened, inflamed, swollen, or damaged).

Injection

- Put on gloves
- Wipe injection site clean with alcohol pads
- Raise a fold of skin between the thumb and forefinger and insert needle as illustrated
- Insert needle as illustrated in adjacent diagram
- Inject drug slowly
- Withdraw needle. Place band-aid over injection site if necessary (*Note: If bleeding occurs, hold pressure on the injection site for 90 seconds or until bleeding stops, and then apply gauze bandage secured by tape*).

***Investigator may, at their judgement, administer antihistamines/NSAIDs to prevent or treat injection site reaction. This must be captured in eCRF.

2.7 AGENT ORDERING

The Responsible Investigational Pharmacy will order study drug from XBiotech's contract drug distributor as needed.

2.8 POTENTIAL DRUG INTERACTIONS

There are no known drug interactions reported with bermekimab.

2.9 PROHIBITED THERAPY

- Phototherapy (PUVA and/or UVB)
- All biologic therapy with a potential therapeutic impact on the HS presented by the patient, including but not limited to the following:
 - \circ Abatacept (Orencia \mathbb{R})
 - Anakinra (Kineret ®)
 - Belimumab (Benlysta ®)
 - Cetolizumab (Cimzia ®)
 - Efalizumab (Raptiva ®)
 - Etanercept (Enbrel ®)
 - o Golimumab (Simponi ®)
 - o Infliximab (Remicade ®)
 - o Natalizumab (Tysabri ®)
 - Rituximab (Rituxan ®)
 - Tocilizumab (Actemra ®)
 - o Ustekinumab (Stelara ®)
- Live virus vaccines (during the study and for 70 days after the last dose of study drug)
- Investigational agents other than bermekimab
- Oral or injectable corticosteroids for treatment of HS except those listed in section 2.11.3 Lesion Intervention
- Oral Analgesics not listed in Section 2.11.1 Analgesic Therapy
- New prescription topical therapies for HS
- Over-the-counter topical washes, creams, soaps, ointments, gels and liquids containing antibacterial agents to treat HS not listed in Section

- 2.10.2 Wound Care
- Surgical or laser intervention for an HS lesion except as outlined in Section 2.11.3 Lesion Intervention

2.10 CONCOMITANT THERAPY

2.10.1 Concomitant Corticosteroid use for Conditions Other than HS

The use of systemic corticosteroids for indications other than HS should be limited to situations for which, in the opinion of the treating physician, there are no adequate alternatives. They should be used on a short-term basis, preferably for ≤ 2 weeks. Longer-term use of corticosteroids should be discussed with the medical monitor or designee and may require discontinuation of study drug. Inhaled, otic, ocular, nasal or other routes of mucosal delivery of corticosteroids are allowed throughout the study.

2.10.2 Wound Care

Subjects are required to use a daily antiseptic wash on their HS lesions. Allowable antiseptic washes are limited to one of the following: soap and water, chlorhexidine gluconate, triclosan, benzoyl peroxide, or dilute bleach in bathwater. Concomitant use of wound care dressings on HS wounds is allowed, however options are limited to alginates, hydrocolloids and hydrogels.

2.11 RESTRICTED THERAPY

2.11.1 Analgesic Therapy

Antihistamine/NSAID use is permitted in this study including those to prevent or treat injection site reaction(s). Most subjects will be required to washout of all opioid analgesics for 14 days prior to baseline or, in the case of non-opioid analgestics, for 24 hours prior to baseline. However, if a subject is on a stable dose of a opioid analgesic medication (PRN is not considered stable), the subject may continue the analgesic, provided the dose is stable for 14 days prior to baseline and is anticipated to remain stable throughout study participation. If a subject's pain (HS-related or non-HS-related) worsens after baseline, they may initiate analgesic therapy at any time as follows:

- Ibuprofen (at a dose of up to 800 mg po every 6 hours) not to exceed 3.2 grams/24 hours; AND/OR acetaminophen as per local labeling.
- If pain is uncontrolled with ibuprofen or acetaminophen at the above dosing regimens after the baseline visit, subjects can be prescribed tramadol (at a dose of up to 100 mg po every 4 hours), not to exceed 400 mg/24 hours.

Dose adjustments of ibuprofen, acetaminophen, or tramadol, and use of these analgesics on an "as needed" (PRN) basis for HS-related pain up to the maximum permitted dose and frequency, are allowed during the study.

From Screening through the end of their study participation, subjects will be required to report to site staff any analgesics taken since their last visit. All analgesics and doses will be captured in the source and on the concomitant medications eCRF.

2.11.2 Antibiotic Rescue Therapy

Concomitant use of oral antibiotic therapy for treatment of HS is not allowed. At Week 4 or Week 8, if a subject experiences an increase in their AN count such that the total count is greaterthanor equalto 150% of their Baseline AN count, antibiotic rescue medication may be initiated. Subjects who qualify may initiate treatment with minocycline or doxycycline up to 100 mg bid. The dosing regimen must remain stable throughout study participation. Otherwise, concomitant use of oral antibiotic therapy for treatment of HS is not allowed. Rescue antibiotic therapy should be captured in the source and on the appropriate eCRF.

2.11.3 Lesion Intervention

In the event that an acutely painful lesion occurs that requires an immediate intervention, physicians will have the option to perform protocol-allowed interventions. Only two types of interventions are allowed: injection with intralesional triamcinolone acetonide suspension (at a concentration of up to 5 mg/mL, up to 1 cc) and incision and drainage.

If incision and drainage is performed, the required over-the-counter antiseptic wash should continue to be used. New systemic and topical therapies following incision and drainage (including antibiotics), are prohibited. Concomitant use of wound care dressings is allowed however options are limited to alginates, hydrocolloids, and hydrogels. Subjects should continue using any ongoing oral and topical therapies (with the constraints as described in Section 2.11 RESTRICTED THERAPY during the study. See Section 9.8 TOXICITY MANAGEMENT for additional discussion on the use of concomitant medications if medically necessitated. Concomitant medications associated with the lesion intervention(s) must be captured in the source and on the appropriate eCRF.

A total of two protocol-allowed interventions are permissible. An intervention can occur on maximally two different lesions at the same visit or on the same lesion at two different study visits. The same lesion cannot be treated two times at the same visit. If a subject requires more than two interventions within the 32 week treatment period, then they must be discontinued from the study treatment.

All study visit evaluations must occur before any interventions are performed. Any lesion that undergoes an intervention will be documented in the source. The site will be required to count any lesion that undergoes an intervention as permanently present from the date of the intervention and must account for it in the source and on the appropriate eCRF.

3. STUDY DESIGN AND OBJECTIVES

This is a randomized, double-blind, placebo-controlled study to further establish the efficacy and safety and explore dose effects for bermekimab monotherapy in adults with moderate-to-severe HS. Approximately 50% of patients enrolled will have failed prior targeted biologic therapy(ies) and approximately 50% will be naïve to these forms of biologic therapy in each arm. Patients will be assessed for study eligibility at the initial screening visit after providing informed consent. Thirty days are allowed in the screening window to complete all screening procedures and randomize the subject. During the screening period, certain treatments will be washed out, as applicable, according to eligibility requirements. Patients who fail initially may be re-screened once based on the investigator discretion but only if inclusion criteria are met at time of rescreening.

The study is approximately 40 weeks (30 day screening period, 32-week treatment period and a 4-week follow-up period) for all subjects.

Patients who meet eligibility criteria at screening will be randomized in a 1:1:1 fashion to one of three treatment arms:

- Arm 1: 800 mg loading dose of bermekimab (2 x 400 mg SC injections) at weeks 0 and 1 followed by weekly (qw) subcutaneous (SC) injections of 400 mg bermekimab through week 31
- Arm 2: 800 mg loading dose of bermekimab (2 x 400 mg SC injections) at weeks 0 and 1 followed by subcutaneous (SC) injections of 400 mg bermekimab every other week (q2w) alternating with matching placebo q2w through week 31.
- Arm 3: 4mL loading dose of placebo (2 x 2mL SC injections) at weeks 0 and 1 followed by weekly placebo injections from weeks 2 through week 15. Patients in Arm 3 will begin to receive weekly (qw) blinded subcutaneous (SC) injections of 400 mg bermekimab beginning at week 16 through week 31.

In order to maintain blinding, all patients will receive two injections at week 0 and 1, followed by weekly injections from weeks 2 to 31. Additionally, at least one qualified individual will be designated at each study site to perform all preparation and injection of the investigational product. The designated injector should have no other contact with the participant during the study, should not discuss the participant's treatment with the participant, participant's caregiver, or other site personnel at any time, and will not be permitted to review the participant's medical records, questionnaires, or the electronic CRF prior to each injection. The designated injector should be documented in the source documents at each visit.

Study treatment will be administered weekly in the clinic for 31 weeks with weekly office visits for 32 weeks. Patients will remain at the study site for a minimum of 30 minutes (+/- 10 minutes) after injections at weeks 0, 1, 2, 16, 17 and 18 injections for safety monitoring.

During the 32-week treatment period, patients will attend weekly clinical study visits. Clinical assessments, collection of samples for bermekimab concentrations, and safety testing will be performed at specified clinic visits. The primary endpoint data will be collected at week 12. After completion of the 36-week study period, data will be locked and analyzed for safety and efficacy endpoints for all arms. In addition to the analyses that will be performed following the formal database lock at the end of the study at Week 36, an additional database lock may be performed at Week 16, and interim analyses utilizing unblinded efficacy data available as the study progresses, may also be conducted to help plan potential future development activities. An internal interim analysis committee (IAC) will be established to review the

interim data and formulate recommended decisions/actions. The IAC will consist of at least a clinician and a statistician (neither of whom are involved in study conduct or compound development), one of whom will chair the committee, and may also include other members as required by the nature of the IAs. Details will be provided in a separate IAC charter, which will define the organization and roles and responsibilities of the committee, possible recommendations or requests, and the communication process following IA reviews. Results from the Week 16 database lock and/or interim analyses will not be disseminated to investigators or subjects participating in the study. In addition, results of the interim analyses will not be disseminated to individuals associated with the conduct of the study.

Patients will be monitored at a follow up visit (visit 34/week 36) for safety and clinical assessments after completing the 32 week treatment period.

The study protocol will be approved by the Institutional Review Board (IRB) or the Ethics Committee (EC) of the participating study sites. Depending on the participating countries both local and central IRB/EC approvals will be granted. The study will be registered at www.clinicaltrials.gov before the enrollment of the first patient. The trial will be conducted in compliance with the protocol, GCP, and all applicable regulatory requirements.

3.1 STUDY ENDPOINTS

Primary Endpoint:

 Proportion of subjects achieving Hidradenitis Suppurativa Clinical Response (HiSCR) at week 12

Secondary Endpoints:

- Change from baseline to week 32 in Numeric Rating Scale for Pain & Itch (NRS Pain & Itch) score
- Change from baseline to week 16 in Numeric Rating Scale for Pain & Itch (NRS Pain & Itch) score
- Change from baseline to week 12 in Numeric Rating Scale for Pain & Itch (NRS Pain & Itch) score

- Change from baseline to week 8 in Numeric Rating Scale for Pain & Itch (NRS Pain & Itch) score
- Proportion of subjects achieving Hidradenitis Suppurativa Clinical Response (HiSCR) at week 32
- Proportion of subjects achieving Hidradenitis Suppurativa Clinical Response (HiSCR) at week 16
- Change in Modified Hidradenitis Suppurativa Score (mHSS), Hidradenitis Suppurativa Physician's Global Assessment (HS-PGA) and Hurley Stage from baseline to week 32
- Change in Modified Hidradenitis Suppurativa Score (mHSS), Hidradenitis Suppurativa Physician's Global Assessment (HS-PGA) and Hurley Stage from baseline to week 16
- Change in Modified Hidradenitis Suppurativa Score (mHSS), Hidradenitis Suppurativa Physician's Global Assessment (HS-PGA) and Hurley Stage from baseline to week 12
- Change in patient reported outcomes from baseline to week 32, including: Hospital Anxiety and Depression Scale (HADS), Dermatology Life Quality Index (DLQI), Health Status Questionnaire (EQ-5D-3L), Patient Global Impression of Change (PGI-c), Patient Global Impression of Severity (PGI-s) and Hidradenitis Suppurativa Symptom Diary (HSSD) HS related Pain Symptom Score in the past 24 hours and total symptom score
- Change in patient reported outcomes from baseline to week 16, including: Hospital Anxiety and Depression Scale (HADS), Dermatology Life Quality Index (DLQI), Health Status Questionnaire (EQ-5D-3L), Patient Global Impression of Change (PGI-c), Patient Global Impression of Severity (PGI-s) and Hidradenitis Suppurativa Symptom Diary (HSSD) HS related Pain Symptom Score in the past 24 hours and total symptom score
- Change in patient reported outcomes from baseline to week 12, including: Hospital Anxiety and Depression Scale (HADS), Dermatology Life Quality Index (DLQI), Health Status Questionnaire (EQ-5D-3L), Patient Global Impression of Change (PGI-c), Patient Global Impression of Severity (PGI-s) and Hidradenitis Suppurativa Symptom Diary (HSSD) HS related Pain Symptom Score in the past 24 hours and total symptom score
- Assessment of Pharmacokinetics (PK)
- Reduction in serum IL-6 from baseline to week 32
- Reduction in serum IL-6 from baseline to week 16
- Reduction in serum IL-6 from baseline to week 12
- Reduction in serum IL-6 from baseline to week 8

Exploratory Endpoints:

- Change from baseline to week 32 in International Hidradenitis Suppurativa Severity Score System (IHS4)
- Change from baseline to week 16 in International Hidradenitis Suppurativa Severity Score System (IHS4)
- Change from baseline to week 32 in Hidradenitis Suppurativa Quality of Life Measure (HiSQOL)
- Change from baseline to week 16 in Hidradenitis Suppurativa Quality of Life Measure (HiSQOL)
- Change from baseline to week 32 in Physician's Global Assessment of Inflammatory Skin Disease (PGA-ISD)
- Change from baseline to week 16 in Physician's Global Assessment of Inflammatory Skin Disease (PGA-ISD)

4. ELIGIBILITY CRITERIA

4.1 INCLUSION CRITERIA

No waivers/exemptions will be granted for protocol inclusion/exclusion criteria.

Subjects are included in the study if they meet all of the following criteria:

- Written informed consent provided by the patient.
- Male or female, age ≥ 18 years.
- Naïve to OR failure of prior targeted biologic therapy for HS (including anti-TNF, anti-IL-17, or JAK inhibitor therapy).
- Must agree to daily use (throughout the entirety of the study) of one of the following over-thecounter treatments to the body areas affected with HS lesions: either soap and water, or a topical antiseptic wash containing chlorhexidine gluconate, triclosan, or benzoyl peroxide, or a dilute bleach bath.
- Diagnosis of HS for at least 1 year prior to screening.
- HS affecting at least two distinct anatomic areas, one of which is Hurley II or III stage.
- A total body count of abscesses and inflammatory nodules (A+N) of at least 3.
- Full understanding of the procedures of the study protocol and willingness to comply with them.

- In case of female patients of childbearing potential, willingness to use one method of contraception of high efficacy during the entire study period. This method can be hormonal contraceptives or one of the following: condoms, diaphragm, or an intrauterine device. Women of non-childbearing potential include those considered to have a medical history that indicates that pregnancy is not a reasonable risk, including post-menopausal women and those with a history of hysterectomy or surgically sterilized.
- Males participating in this clinical research study should not get a sexual partner pregnant during participation in this research study as the effect of the study drug on sperm is not known.

4.2 EXCLUSION CRITERIA

Subjects with ANY of the following will be excluded from the study:

- Age below 18 years.
- History of treatment with bermekimab for any reason.
- Receipt of oral antibiotic treatment for HS within 28 days prior to baseline.
- Receipt of prescription topical therapies for the treatment of HS within 14 days prior to baseline
- Receipt of systemic non-biologic therapies for HS (immunosuppressants, corticosteroids, retinoids, or hormonal therapies) within 28 days prior to screening.
- Subject has been treated with any drug of chemical or biologic nature within a minimum of 30 days or 5 half-lives (whichever is longer) of the drug prior to baseline.
- History of severe allergic or anaphylactic reactions to human, humanized, chimeric, or murine monoclonal antibodies.
- Has received a live (attenuated) vaccine over the 28 days prior to screening.
- If entering the study on a dose of opioid analgesics that has not been stable for at least 14 days prior to baseline visit (PRN is not considered a stable dose).
- Subject received non-opioid analgesics within 24 hours of baseline visit.
- Subject has a draining fistula count of greater than 20 at baseline.
- Major surgery (requiring general anesthesia or respiratory assistance) within 28 days prior to Day 0 of start of study drug.
- Hepatic dysfunction defined as any value of transaminases, of γ-glutamyl transpeptidase (γGT) or of total bilirubin > 3x upper normal limit.

- Known or suspected history of immunosuppression, including history of invasive opportunistic infections (e.g. tuberculosis [TB], histoplasmosis, listeriosis, coccidioidomycosis, pneumocystosis, aspergillosis) despite infection resolution.
- Stage C Child-Pugh liver cirrhosis.
- History of human immunodeficiency virus (HIV) or active infection with hepatitis B virus (HBV) or hepatitis C virus (HCV).
- Neutropenia defined as <1,000 neutrophils/mm³.
- Pregnancy or lactation.

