5.3 DISCONTINUATION OF THERAPY

If a patient is discontinued from study, the reason for discontinuation/withdrawl must be clearly documented in the source documentation and the EDC. Every effort should be made by the investigative site to have subjects who discontinue early from study complete all assessments included in the Early Termination visit included in the study calendar provided in section 5. All subjects will be unblinded after clinical database lock.

Study therapy MUST immediately be discontinued for any the following reasons:

- Withdrawal of informed consent (subject's decision to withdraw for any reason)
- Any clinical adverse event, laboratory abnormality, inter-current illness, or clinical progression of disease which, in the opinion of the Principal Investigator, indicates that continued participation in the study is not in the best interest of the subject
- Pregnancy
- Termination of the study by the sponsor
- Imprisonment or the compulsory detention for medical treatment.
- Initiating treatment with prohibited therapies (see section 2.9)....

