10.5.3.1 Primary Efficacy Analysis

For the primary efficacy endpoint, the two bermekimab treatment groups will be compared with placebo. To account for these two comparisons, testing will be done in a sequential manner, each at the 0.05 alpha level. The bermekimab weekly injection group (Treatment Arm 1) will be compared to the placebo group (Treatment Arm 3) first. If this test is significant at the 0.05 level, then the bermekimab every other week injection group (Treatment Arm 2) will be compared to the placebo group (Treatment Arm 3). Otherwise, the P-value for Treatment Arm 2 vs Treatment Arm 3 will be considered nominal. This method to control the type-1 error will only be implemented for the primary efficacy analysis variable.

The number and percentage of patients who have a positive HiSCR score (achiever) at week 12 will be presented by treatment group. Patients who terminate from the study early prior to week 12 will count as non-responders (non-achievers) in the primary efficacy analysis (Non-Responder Imputation). If a patient received rescue medication, the patient will be counted as a non-responder from the start of rescue medication. Additional treatment failure rules and sensitivity analyses will be discussed in the statistical analysis plan.

A Cochran-Mantel-Haenszel (CMH) general association test stratified by prior anti-tumor necrosis factor or IL-17 inhibitor therapy use (yes/no) and Hurley Stage (II/III) will be used to compare each bermekimab dose separately with placebo. The primary efficacy analysis population will be the mITT population.

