# 5.2.2. Data Handling Rules

No imputation will be performed for missing baseline values.

For the main analysis of primary endpoint of HiSCR at Week 12, participants who discontinued treatment will be considered as a non-responder from that point onward. The remaining missing data will be imputed as non-responder. Supplementary analyses will be performed and include (1) using observed data regardless of whether the participant discontinued treatment or have missing data, and (2) data after treatment discontinuation will be considered as missing, missing response will be imputed by multiple imputation methods under the assumption of missing at random. Similar data handling rules (i.e., main analysis with non-responder imputation and

2 supplementary analyses) will also be applied for HiSCR response over time through Week 16. The following data handling rules will be applied for other endpoints:

Binary secondary endpoints:

• Analyses will be similar to the main analysis of the primary endpoint. A participant who discontinued treatment will be considered as a non-responder from that point onward. The remaining missing data will be imputed as non-responder.

Continuous secondary endpoints:

- If a participant discontinued treatment, zero will be assigned to improvement or percent improvement. Remaining missing data will not be imputed. A MMRM model will adjust for missing post baseline data and all available data from the 3 treatment groups through Week 16 or from Week 16 through Week 36 will be included. Under the assumption of missing at random (MAR), the missing data will be accounted for through correlation of repeated measures in the model.
- In addition, supplementary analyses will be performed for the analyses related to (a) change from baseline in AN count (Section 5.4.3.2.2) and (b) change from baseline in HSSD past 24 hours pain (Section 5.4.3.5.3.2) endpoints using
  - Observed data regardless of whether the subject discontinued treatment or have missing data.
    - Data after treatment discontinuation will be considered as missing, missing data will be addressed by MMRM model.

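### Three of the four systemic HS drug classes washed out at entry are not prohibited on study, and starting one does not stop a Week 12 HiSCR from counting as a response

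*Protocol*

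**What the plan says.** **Before Day 0.** Protocol 4.2 excludes "Receipt of systemic non-biologic therapies for HS (immunosuppressants, corticosteroids, retinoids, or hormonal therapies) within 28 days prior to screening". The next criterion is wider: "Subject has been treated with any drug of chemical or biologic nature within a minimum of 30 days or 5 half-lives" (whichever is longer) before baseline. Section 5.1 has eligibility checked again at Week 0, so the pre-baseline period is covered.

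**On study.** Of the four classes, section 2.9 lists one: "Oral or injectable corticosteroids for treatment of HS except those listed in section 2.11.3 Lesion Intervention". Its other entries include biologics, phototherapy, investigational agents, new prescription topicals, and surgery or laser. Section 2.11.2 bars oral antibiotics for HS except as rescue. Section 2.11.3 bars new systemic therapy, but only after incision and drainage. Section 5.3 makes discontinuation mandatory for "Initiating treatment with prohibited therapies (see section 2.9", so that trigger reaches no further than the 2.9 list.

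**In the analysis.** Protocol 10.5.3.1 says "If a patient received rescue medication, the patient will be counted as a non-responder from the start of rescue medication" and then "Additional treatment failure rules and sensitivity analyses will be discussed in the statistical analysis plan". The only rescue medication the protocol defines is the antibiotic in 2.11.2, where "antibiotic rescue medication may be initiated" once the AN count meets a threshold. SAP 5.2.2 says "participants who discontinued treatment will be considered as a non-responder from that point onward" and imputes remaining missing data as non-response. SAP 5.3.3 repeats both rules for Week 12. SAP 5.3.2 puts antibiotic rescue and lesion intervention inside the treatment regimen and names treatment discontinuation as the only intercurrent event.

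**The concern.** The entry criteria treat these four classes as HS treatments that would confound the response. After Day 0 the protocol keeps that position for one of them. A newly started retinoid, immunosuppressant or hormonal HS drug is then neither part of the regimen nor an intercurrent event, so the estimand does not say what to do with the patient. The scoring rules decide by default: a patient who stays on study drug and has lesion counts at Week 12 is scored on those counts.

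At stake is what a Week 12 response means in a trial described as bermekimab monotherapy. With equal use across arms, or more use on placebo, the treatment difference shrinks and power is lost. The gap does not by itself create a false positive.

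**Working it through.** **1. Does any clause close the gap?**

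| Clause | What it covers | Reaches the three classes? |
|---|---|---|
| Protocol 2.9 | Corticosteroids for HS, biologics, topicals and others | No |
| Protocol 2.11.2 | Oral antibiotics for HS | No |
| Protocol 2.11.3 | New systemic therapy after incision and drainage | Only in those patients |
| Protocol 5.3 | Mandatory stop tied to the 2.9 list; clinical progression at investigator's judgement | Only by discretion |
| Protocol 10.5.3.1 | Rescue medication (only antibiotics are defined) | Not as defined |
| SAP 5.2.2, 5.3.3 | Discontinuation, missing data | No |
| SAP 5.3.2, supplementary estimands | Change only the strategy for discontinuation | No |
| SAP 2.4.1.2, per-protocol set | AN count, fistula count, missed doses | No |
| SAP 4.6 | Summary and listing of treatments that could improve HS | Makes use visible, but no HiSCR analysis acts on it |

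**2. The plan's own figure.** Inputs from Protocol 10.1 and SAP 1.4: 60% vs 30%, two-sided 0.05, Pearson chi-square, 42 per arm for about 80% power, about 150 randomized 1:1:1 (50 per arm). Normal approximation with pooled null variance, where p̄ is the mean of the two rates:

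power = Φ{ [d√n − 1.96·√(2p̄(1−p̄))] / √(p1(1−p1) + p0(1−p0)) }

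With d = 0.30 and p̄ = 0.45, √(2 × 0.45 × 0.55) = 0.7036 and √(0.24 + 0.21) = 0.6708.

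- n = 42: (1.944 − 1.379)/0.6708 = 0.843, power 0.80. The stated figure reproduces.
- n = 50: (2.121 − 1.379)/0.6708 = 1.107, power 0.87.

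**3. Illustration.** Assumed values, because the documents give no uptake rate: a fraction f of would-be non-responders start such a drug, and a fraction r of those reach HiSCR.

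- Placebo: p0 = 0.30 + 0.70·f·r
- Arm 1, if it has uptake too: p1 = 0.60 + 0.40·f·r

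With r = 0.5:

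| f | p0 | p1 | Equal uptake: difference (points) | Power, n=50 / n=42 | Placebo only: difference (points) | Power, n=50 / n=42 |
|---|---|---|---|---|---|---|
| 0 | 0.300 | 0.60 | 30.0 | 0.87 / 0.80 | 30.0 | 0.87 / 0.80 |
| 0.05 | 0.3175 | 0.61 | 29.25 | 0.85 / 0.78 | 28.25 | 0.82 / 0.75 |
| 0.10 | 0.335 | 0.62 | 28.5 | 0.82 / 0.75 | 26.5 | 0.76 / 0.69 |
| 0.20 | 0.370 | 0.64 | 27.0 | 0.78 / 0.70 | 23.0 | 0.64 / 0.56 |

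Expected extra responders per 50 patients: placebo 50 × 0.70 × f × 0.5 = 0.9, 1.8, 3.5; Arm 1 50 × 0.40 × f × 0.5 = 0.5, 1.0, 2.0.

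With the milder r = 0.3 and equal uptake, power at n = 50 is 0.854, 0.841 and 0.815 for f = 0.05, 0.10 and 0.20.

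**4. After the fix.** If starters come only from patients who would not otherwise respond, counting them as non-responders returns the rates to 60% and 30%, and power to 0.80 at 42 per arm and 0.87 at 50.

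**The case against.** The gap is narrow. Section 2.9 bars much else, including all biologics with potential HS impact. Section 4.1 lists JAK inhibitors under targeted biologic therapy, so that ban arguably reaches them too. The protocol sets out what may be done when HS worsens (named analgesics, threshold-based antibiotics, two kinds of lesion intervention), and the design is described as monotherapy. Adding a systemic HS drug would go against evident intent. An investigator may stop treatment for progression, which makes the patient a non-responder. Rescue medication in 10.5.3.1 could be read broadly. The SAP 4.6 listing would identify affected patients.

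The size is also assumed. A 50% response among would-be non-responders with less than 12 weeks on the added drug is generous. The 20% case means 50 × 0.70 × 0.20 = 7 placebo starters, and placebo-only uptake is an extreme in a blinded trial. At 50 per arm, equal uptake of 5% or 10% leaves power above 80%. Finally, scoring patients as observed after an added drug is in effect a treatment-policy approach, which can be defended.

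The points on size stand: the loss may well be small. The backstops do not close the gap. Intent is not a ban, the progression clause is discretionary, the broad reading of rescue is not carried into the SAP, and a listing does not change a response status. A treatment-policy approach to added drugs would be acceptable if chosen, but SAP 5.3.2 does not choose it.

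**Conclusion.** The concern holds. Followed exactly, the plan credits a Week 12 HiSCR reached after starting a retinoid, a non-biologic immunosuppressant or a hormonal HS drug to the randomized arm in the main analysis, and no supplementary or per-protocol analysis acts on that drug use. The exception is a patient who has had incision and drainage, for whom new systemic therapy is prohibited.

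The textual finding needs no assumption; the size does. For 5% to 20% uptake among would-be non-responders with half of them responding, the loss of power at 50 per arm is about 2 to 9 percentage points with equal uptake and 5 to 23 with placebo-only uptake. The upper end of the second range is an extreme case. Real uptake cannot be judged from the documents.

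**What to change.** 1. In SAP 5.2.2, 5.3.2 and 5.3.3, make the start of a systemic non-biologic HS therapy (the classes in 4.2) between baseline and Week 12 an intercurrent event under the composite strategy. The patient is a non-responder from that date, identified from the concomitant medication records. Keep the present rule as a supplementary analysis.
2. In Protocol 2.9, add systemic non-biologic immunosuppressants, retinoids and hormonal therapies for HS, with an explicit exemption for hormonal contraception, which 4.1 accepts. Section 5.3 then applies to them. The SAP rule is still needed for patients who start such a drug and are not discontinued.

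Set the rule before the Week 16 lock, at which SAP 1.5.2 unblinds some sponsor staff; deciding later which drugs cancel a response would be post hoc. If an amendment is impractical, the SAP change alone protects the main analysis.

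The cost is a few lines of SAP text and a short amendment. Concomitant medications are already recorded, and SAP 4.6 already identifies those that could improve HS. The indication of each hormonal drug must be checked to separate contraception from HS treatment, and the documents do not say that indication is collected. Observed response rates may be slightly lower.
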